6.13.1.4. Discontinuation From Study Drug Due to Adverse Event

The number and percentage of patients who prematurely discontinue study drug due to an AE will be summarized by treatment using MedDRA PT nested within SOC. Events will be ordered by decreasing frequency within SOC. Time-to-event analyses will be conducted by treatment on time to study drug discontinuation.

6.13.1.5. Treatment of Overdose

A listing of patients reporting over-dosing of tirzepatide will be provided as a protocol deviation.

6.13.2. Special Safety Topics

6.13.2.1. Hypoglycemic Events

Definitions of different categories of hypoglycemic events are included in [Table GPGK.6.3](#).

Table GPGK.6.3. Definitions of Hypoglycemic Event Categories

	Symptoms and/or Signs of Hypoglycemia	Blood Glucose Level
Glucose Alert Value:		
Documented symptomatic hypoglycemia	Yes	≤ 70 mg/dL (3.9 mmol/L)
Documented asymptomatic hypoglycemia	No	≤ 70 mg/dL (3.9 mmol/L)
Documented unspecified hypoglycemia	Unknown	≤ 70 mg/dL (3.9 mmol/L)
Clinically Significant Hypoglycemia (Level 2):		
Documented symptomatic hypoglycemia	Yes	< 54 mg/dL (3.0 mmol/L)
Documented asymptomatic hypoglycemia	No	< 54 mg/dL (3.0 mmol/L)
Documented unspecified hypoglycemia	Unknown	< 54 mg/dL (3.0 mmol/L)
Severe Hypoglycemia (Level 3)		

Severe hypoglycemia: Defined as an episode with severe cognitive impairment requiring the assistance of another person to actively administer carbohydrate, glucagon, or other resuscitative actions. Severe hypoglycemia will be reported as an SAE. Severe hypoglycemia will be considered as AESI.

Nocturnal hypoglycemia: Defined as any hypoglycemic event that occurs between bedtime and waking.

To avoid duplicate reporting, all consecutive blood glucose (BG) values ≤ 70 mg/dL (3.9 mmol/L) occurring within a 1-hour period may be considered to be a single hypoglycemic event.

Statistical summaries and analyses will exclude hypoglycemic events occurring after initiation of a new antihyperglycemic therapy. For severe hypoglycemia and level 2 hypoglycemia, incidence as well as rate per patient year of exposure will be provided by treatment at specified time intervals. A listing of hypoglycemic events will also be provided.

The incidence of hypoglycemic event will be analyzed using logistic regression with treatment and stratification factors as fixed effects. The rate of hypoglycemic episodes per patient year may

be analyzed using a generalized linear mixed-effects model assuming the number of hypoglycemic episodes follows a negative binomial distribution with the mean modeled using stratification factors and treatment as fixed effects. When the number of hypoglycemic events is less than 10, a listing of hypoglycemic events will be provided instead.

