Patients will be permitted to use concomitant medications that they require during the study, except certain medications that may interfere with the assessment of efficacy and safety characteristics of the study treatments. Antihyperglycemic medications other than study drugs are not allowed at any time during the study except as allowed for rescue therapy, after early study drug discontinuation, or short-term insulin use. Rescue therapy with other glucose-lowering agents may be medically indicated in certain situations after randomization due to severe, persistent hyperglycemia or early discontinuation of study treatment. Metformin will be the first choice of therapy unless contraindicated. Glucagon-like peptide-1 receptor agonists, dipeptidyl peptidase-4 (DPP-4) inhibitors, and pramlintide are prohibited medications and are not

allowed as rescue therapies. Short-term insulin use for up to 14 days is allowed for certain clinical situations (for example, elective surgery, during hospitalization, hyperosmolar states). If insulin is prescribed as a rescue therapy, it must be differentiated from short-term use of insulin therapy for medical emergencies when reported in the eCRF.

Patients who develop severe, persistent hyperglycemia based on prespecified thresholds (see Sections 7.8.2.3 and 9.2.2.2) will receive a new glucose-lowering intervention (“rescue therapy”) and will also continue to administer study drug. Patients who need hyperglycemic rescue therapy will continue in the trial until they complete all study visits.

Study governance considerations are described in detail in [Appendix 3](#).

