7.8.2.4. Management of Patients Permanently Discontinuing Study Drugs

Circumstances under which patients may be required to prematurely discontinue study drug are outlined in Section 8.1. Patients who stop the study drug permanently will continue participating in the trial according to the protocol to collect all planned efficacy and safety measurements and should receive another glucose-lowering intervention (Section 7.4.2). The new glucose-lowering intervention will be recorded on the eCRF specified for collecting antihyperglycemic medications.

To assure timely initiation of another antihyperglycemic medication after permanent discontinuation of study drug, patients should be advised to promptly notify the site when this

situation occurs. The investigator should evaluate the need for additional antihyperglycemic medication at this time (as outlined in Section 7.4.2) and initiate the additional intervention accordingly. An unscheduled visit should be used as needed for more timely initiation if warranted based on the investigator's clinical judgment.

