Patients who stop the study drug permanently will receive another glucose-lowering intervention and will continue participating in the trial according to the protocol to collect all planned efficacy and safety measurements. The new glucose-lowering intervention will be recorded on the eCRF specified for collecting antihyperglycemic medications.

Patients discontinuing from the investigational product prematurely for any reason should complete adverse event and other follow-up procedures per Section 2 (Schedule of Activities), Section 9.2 (Adverse Events), and Section 9.4 (Safety) of this protocol.

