10.1. Sample Size Determination

Patients will be randomized in a 1:1:1:1 ratio to tirzepatide 5 mg, 10 mg, 15 mg, or placebo.

The trial is powered to assess superiority of tirzepatide 5 mg, 10 mg, or 15 mg versus placebo in parallel relative to mean change from baseline in HbA1c at 40 weeks under the following assumptions:

- use of 2-sample t-test to compare treatment means utilizing HbA1c data collected before initiation of any rescue medication and premature treatment discontinuation;
- up to 25% patients in tirzepatide arms and up to 35% patients in placebo arm initiating any rescue medication or premature treatment discontinuation;
- at least 0.65% (placebo adjusted) mean reduction in HbA1c for the tirzepatide doses; and
- a common standard deviation (SD) of 1.1%.

On the basis of these assumptions, randomizing 472 patients using a 1:1:1:1 randomization ratio to tirzepatide 5 mg (118 patients), tirzepatide 10 mg (118 patients), tirzepatide 15 mg (118 patients), and placebo (118 patients) will provide at least 90% power to establish superiority for a tirzepatide dose compared to placebo at a 2-sided significance level of 0.017. Furthermore, this sample size will ensure at least 90% power for the HbA1c superiority evaluation utilizing all available HbA1c data at 40 weeks with missing data imputed with a conservative multiple imputation method (as described in the Efficacy Analyses [Section 10.3.3] below), provided that the mean reduction in HbA1c for the tirzepatide doses is at least 0.65% (placebo adjusted) and SD increases to no more than 1.3% due to the inclusion of data on rescue medications, inclusion of data after premature treatment discontinuation, and missing data imputation.

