10.3.4. Safety Analyses

Unless specified otherwise, safety assessments will be guided by an estimand comparing safety of tirzepatide doses with placebo irrespective of adherence to study drug or initiation of rescue therapy. Thus, safety analyses will be conducted using the SS. Selected safety analyses may be conducted after excluding data on rescue therapy or data after starting another antihyperglycemic medication.

Adverse events will be coded from the actual term using the Medical Dictionary for Regulatory Activities (MedDRA) and reported with preferred terms and system organ class. Selected notable AEs of interest may be reported using high-level terms or Standardized MedDRA Queries. Summary statistics will be provided for incidence of TEAEs, SAEs, study discontinuation due to AEs, study drug discontinuation due to AEs, deaths, and other CV endpoints. Counts and proportions of patients experiencing AEs will be reported for each treatment group, and Fisher’s exact test will be used to compare the treatment groups.

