6.10. Treatment Exposure and Compliance

Listing of patients randomized but not receiving study treatment will be provided, if applicable. The listing will include patient identification, randomized treatment arm, and the reason for not receiving study treatment.

Summary of duration to end of the study (defined as time in days from date of randomization to date of safety follow-up or date of early study discontinuation) and duration on study treatment (defined as time in days from date of first dose of study treatment to date of last dose of study treatment plus 7 days) will be provided by study treatment.

6.10.1. *Exposure and Compliance to Tirzepatide*

Number of patients prematurely discontinuing study treatment prior to the 40-week visit will be provided by study treatment. Reasons for prematurely discontinuing study treatment prior to the 40-week visit will be provided by study treatment. Time-to-event analysis of premature study treatment discontinuation will be conducted.

If data warrant, proportion of patients receiving 2.5 mg, 5 mg, 7.5 mg, 10 mg, 12.5 mg or 15 mg for tirzepatide treatment groups may be presented by randomized treatment and time intervals from first dose. A listing of patients who re-initiate due to missing ≥ 3 consecutive doses may be produced.

Overall treatment compliance will be defined as taking at least 75% of the scheduled tirzepatide doses. Compliance will be calculated by taking the number of doses administered (regardless of the actual dose administered) divided by the total number of doses expected to be administered $\times 100$. Overall treatment compliance will be summarized descriptively by treatment using the mITT Population.

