6.13. Safety Analysis

Unless specified otherwise, safety assessments will be based on the SS (see [Table GPGK.6.1](#)). All events that occur between the date of first dose of study drug to the date of patient's safety

follow-up visit or patient's end of study participation will be included. For assessing benefit and risk profile through 40-weeks, selected safety analyses may be conducted by utilizing safety data from first dose through the date of 40-week visit. For rare events (<10 patients have the events), summary tables may not be generated, and individual patient level data will be listed.

Unless specified otherwise, comparisons of tirzepatide doses to placebo will be performed.

For selected continuous safety parameters, difference among treatment mean change from baseline at scheduled visits will be assessed via a MMRM using REML. The model will include country/pooled country, baseline HbA1c ($\leq 8.5\%$, $>8.5\% [\leq 69, >69 \text{ mmol/mol}]$), past OAM use (Yes or No), treatment group, visit, and treatment-by-visit interaction as fixed effects, and baseline value of the safety parameter as a covariate. To model the covariance structure within patients, the unstructured covariance matrix will be used. If this model fails to converge, the covariance structures specified in Section 6.12.1.1 will be tested in order.

For selected safety parameters, time-to-first-event analysis via cox-proportional hazards model may be conducted. For patients experiencing an event, "time-to-first-event" will be the time (in weeks) to the first occurrence of the event. For patients without the event, "time-to-event" will be censored at end of study participation (study discontinuation, safety follow-up visit, or date of death).

Where specified, rate of events will be analyzed using a generalized linear mixed-effects model assuming the number of events follow a negative binomial distribution, and with treatment as a fixed effect. The logarithm of years in specified time interval will be adjusted as an offset to account for possible unequal treatment duration in specified time interval between patients.

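### SAP 6.13.2.1 makes an optional exclusion of hypoglycemic events universal, and does not tie person-time to the window in which events count (minor)

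*SAP*

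**What the plan says.** **Event rule.** SAP 6.13.2.1: "Statistical summaries and analyses will exclude hypoglycemic events occurring after initiation of a new antihyperglycemic therapy". The same paragraph promises, for severe and level 2 hypoglycemia, incidence and a rate per patient-year of exposure over specified time intervals, and a listing of events. The rate model is optional, and with fewer than 10 events a listing replaces the analysis.

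**Person-time.** SAP 6.13 defines the model offset as the logarithm of years in an interval that it does not define, which "will be adjusted as an offset to account for possible unequal treatment duration in specified time interval between patients". The only treatment duration that the SAP defines is in 6.10: "time in days from date of first dose of study treatment to date of last dose of study treatment plus 7 days".

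**Default event window.** SAP 6.13 counts events from first dose to the safety follow-up visit or end of participation. A cut at the 40-week visit is offered only for selected analyses. The safety analysis set (SS, Table GPGK.6.1) covers Study Periods II and III whether or not a new antihyperglycemic medication was started.

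**Protocol rule.** Section 10.3.4 bases safety on all data, irrespective of adherence or rescue, and adds: "Selected safety analyses may be conducted after excluding data on rescue therapy or data after starting another antihyperglycemic medication". Section 10.3.4.1 repeats for hypoglycemia that some analyses may exclude such data.

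**Who starts new therapy.** Under Protocol 5.1, patients with severe, persistent hyperglycemia receive rescue "and will also continue to administer study drug". For patients who stop study drug, 8.1.1 says: "Patients who stop the study drug permanently will receive another glucose-lowering intervention and will continue participating in the trial according to the protocol". Section 7.8.2.4 instead says: "The investigator should evaluate the need for additional antihyperglycemic medication at this time".

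**The concern.** There are two separate issues.

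1. **Scope of the exclusion.** The protocol offers it as an option for some analyses; the SAP applies it to every hypoglycemia summary and analysis. Occurrence of hypoglycemic episodes is a stated safety objective. A non-serious level 2 event after new therapy appears in no level 2 incidence or rate. A listing is not an incidence, and adverse event tables by preferred term do not identify level 2.

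2. **Numerator and denominator.** A rate is interpretable only if the denominator is the time in which an event could have been counted. Here the event window is stated and the person-time window is not. If exposure is taken as treatment duration, time after rescue stays in the denominator although no event can count there. At the same time, the weeks between end of treatment and safety follow-up are outside the denominator although events there do count. The two errors act in opposite directions. If the arms differ in how many patients start new therapy, the error differs between arms and the rate ratio moves.

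**Working it through.** The documents give no hypoglycemia rate or exposure figure, so there is no plan figure to reproduce. The check asks how far the rate ratio could move under each reading of exposure.

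**Inputs from the documents**
- Share with rescue or premature discontinuation (Protocol 10.1): "up to 25% patients in tirzepatide arms and up to 35% patients in placebo arm initiating any rescue medication or premature treatment discontinuation". These are planning upper limits. They are used as f = 0.25 (tirzepatide) and f = 0.35 (placebo).
- Treatment period 40 weeks, safety follow-up at week 44. Last dose at week 39 (Schedule of Activities, footnote x), so last dose + 7 days is week 40 for completers.

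**Assumptions**
- Constant event rate; everyone in the share f starts new therapy at week t = 20 in both arms.
- A fraction s of them (0.25, 0.50 or 0.75) are rescued and stay on study drug to week 40. The rest stop study drug at week t, so their treatment duration ends at t + 1.

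**Formulas (weeks per patient)**
- Countable time, events to week E: C = (1 − f)·E + f·t
- Treatment duration: D = (1 − f)·40 + f·s·40 + f·(1 − s)·(t + 1)
- Reported rate ÷ true rate = C/D. The rate ratio is multiplied by (C/D for tirzepatide) ÷ (C/D for placebo).

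**Reading A: exposure is treatment duration, events to week 44 (the SAP default window)**

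C = 0.75·44 + 0.25·20 = 38.0 (tirzepatide); 0.65·44 + 0.35·20 = 35.6 (placebo).

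| s | D tirzepatide | D placebo | Rate error, tirzepatide | Rate error, placebo | Ratio multiplied by |
|---|---|---|---|---|---|
| 0.25 | 36.44 | 35.01 | +4.3% | +1.7% | 1.03 |
| 0.50 | 37.63 | 36.68 | +1.0% | −2.9% | 1.04 |
| 0.75 | 38.81 | 38.34 | −2.1% | −7.1% | 1.05 |

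**Reading B: same exposure, events limited to week 40 (optional in SAP 6.13)**

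C = 35.0 and 33.0 with the same D. The ratio is multiplied by (35.0/36.44)/(33.0/35.01) = 1.02, (35.0/37.63)/(33.0/36.68) = 1.03 and (35.0/38.81)/(33.0/38.34) = 1.05.

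**Reading C: exposure is full follow-up (44 weeks for all)**

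The ratio is multiplied by (38.0/44)/(35.6/44) = 38.0/35.6 = 1.07.

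**Reading D: exposure is cut at new therapy and otherwise runs as long as events count**

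C = D in both arms. The factor is 1.00.

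**Sensitivity**
- Half the shares (0.125 and 0.175): 1.01 to 1.02 under A and under B; under C, 41.0/39.8 = 1.03.
- Start at week 32, s = 0.50, upper-limit shares: (41.0/39.13)/(39.8/38.78) = 1.02 under A; (38.0/39.13)/(37.2/38.78) = 1.01 under B.
- If nobody who stops study drug starts new therapy, their events count to week 44 and C = (1 − f)·44 + f·s·20 + f·(1 − s)·44. Under A the factor is (42.5/36.44)/(41.9/35.01) = 0.97 at s = 0.25 and (39.5/38.81)/(37.7/38.34) = 1.03 at s = 0.75. The direction is therefore not fixed.

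**Sampling error for scale.** With 25 events per arm (assumed), the 95% limits on a rate ratio extend by a factor of exp(1.96·√(1/25 + 1/25)) = 1.74 either way.

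**The case against.** **The SAP breaks no rule.** The all-data default applies unless specified otherwise in both documents, and 6.13.2.1 does specify otherwise. Protocol 10.3.4.1 permits the exclusion for hypoglycemia by name. SAP 6.2 allows a change to be justified in the SAP or in the clinical study report. This stands, so a reader should not infer a breach of protocol. What remains is that the protocol allows the exclusion for some analyses, the SAP applies it to all, and neither 6.13.2.1 nor the revision history gives a reason.

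**The exclusion is sensible.** Rescue can include insulin, and removing later events helps isolate the study drug. This stands as a reason to keep the excluding analysis, but not to make it the only one.

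**Exposure is unstated, not misstated.** The protocol speaks of excluding data, which can include person-time, and an interval ending at new therapy fits the SAP wording. The duration in 6.10 serves an exposure summary, and 6.13.2.1 does not cite it. This stands too: the gap is one of specification.

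**A stronger reading to avoid.** A reader might infer that uncut exposure makes the rates too low in general. The documents do not support that. Reading A, which uses the SAP's own event window, gives errors of both signs. Uniform understatement needs a week-40 event cut, which the SAP leaves optional, or full follow-up as the denominator, which it does not state.

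**It changes no conclusion.** Incidence and its logistic regression use no person-time, the rate model is optional, and the comparisons are not multiplicity-controlled. This is why the point is minor.

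**Conclusion.** The point holds as a minor one, in two parts.

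The firmer part is the scope of the exclusion. As the SAP stands, non-serious level 2 events have no incidence or rate under the protocol's default safety estimand. Severe events are not lost, because they are reported as serious adverse events and summarized in the SS. This part does not depend on any calculation.

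The second part is the unmatched person-time. At the protocol's upper-limit shares and an assumed common week-20 start, with everyone in those shares starting new therapy, the rate ratio is multiplied by about 1.02 to 1.05 if exposure is treatment duration, by about 1.07 if it is full follow-up, and by 1.00 if exposure is cut to match the events. Individual arm rates can be slightly too high or too low. The shift shrinks with smaller shares or later starts. Its direction depends on the start being equally timed in both arms and on how many patients who stop study drug begin another agent. Protocol 8.1.1 and 7.8.2.4 word that last point differently and should be reconciled. All these shifts are small beside a sampling factor of 1.74.

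**What to change.** (a) Add one supplementary table to SAP 6.13.2.1: incidence and rate of level 2 and severe hypoglycemia by arm, using all events and full exposure in the SS. Its downside is that it mixes in the effects of the added therapy, so it should stand beside the excluding analysis and not replace it.

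(b) State in SAP 6.13.2.1 that, in the excluding analysis, patient-years and the model offset cover exactly the window in which events count: from first dose to the start of a new antihyperglycemic therapy or, without one, to the same end date as is used for events.

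The cost is two sentences of SAP text, one derived exposure variable and one table. Data collection, trial conduct and patient management are unchanged.

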5.2. Number of Participants

A total of approximately 472 patients (118 patients per treatment group) will be randomized.

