10.3. Statistical Analyses

10.3.1. General Statistical Considerations

Statistical analysis of this study will be the responsibility of Lilly or its designee. Any change to the data analysis methods described in the protocol will require an amendment ONLY if it changes a principal feature of the protocol. Any other change to the data analysis methods described in the protocol, and the justification for making the change, will be described in the statistical analysis plan (SAP) or the clinical study report. Additional exploratory analyses of the data may be conducted as deemed appropriate.

Unless otherwise noted, all tests of treatment effects will be conducted at a 2-sided alpha level of 0.05, and the confidence interval will be calculated at 95%, 2-sided. In statistical summaries and analyses, patients will be analyzed as randomized.

There will be 2 estimands of interest in comparing efficacy of tirzepatide doses with placebo. First estimand, the “efficacy” estimand, represents efficacy prior to discontinuation of study drug without confounding effects of antihyperglycemic rescue therapy. Second estimand, the “treatment-regimen” estimand, represents the efficacy irrespective of adherence to study drug or initiation of rescue antidiabetic drugs.

The primary efficacy assessment, guided by the “efficacy” estimand, will be conducted using the efficacy analysis set (EAS). The primary efficacy assessment, guided by the “treatment-regimen” estimand, will be conducted using the full analysis set. As they are intended for different purposes, no multiplicity adjustments will be made for conducting 2 primary efficacy assessments relative to efficacy and treatment-regimen estimands.

Unless specified otherwise, safety assessments will be guided by an estimand comparing safety of tirzepatide doses with placebo irrespective of adherence to study drug or initiation of antihyperglycemic rescue therapy. Thus, safety analysis will be conducted using the safety analysis set (SS). Selected safety analyses may be conducted after excluding data on rescue therapy or data after starting another antihyperglycemic medication.

Summary statistics for continuous measures will include sample size, mean, SD, median, minimum, and maximum. The analysis model to make comparisons among treatment groups relative to continuous measurements assessed over time will be a mixed model for repeated measures (MMRM) with terms:

- treatment,
- visit,
- treatment-by-visit interaction,

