- country,
- any past prior use (yes or no) of any oral antidiabetic medication,
- baseline HbA1c category [$\leq 8.5\% (\leq 69 \text{ mmol/mol})$ or $> 8.5\% (> 69 \text{ mmol/mol})$],
- and baseline measurement as a covariate.

For analyses with HbA1c, the baseline HbA1c category will not be included in the model. An unstructured covariance structure will model the relationship of within-patient errors.

The Kaplan-Meier method will be used for estimation of cumulative event-free survival rates over time, and cox proportional hazards regression analysis will be used to compare hazard rates among treatments.

Summary statistics for categorical measures (including categorized continuous measures) will include sample size, frequency, and percentages. Fisher's exact test will be used to examine the treatment difference in categorical outcomes. Logistic regression may be used to examine the treatment difference in binary efficacy outcomes. The negative binomial regression model will be used for the treatment comparison of discrete count measures if deemed appropriate.

Other statistical methods may be used, as appropriate, and details will be documented in the SAP.

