End of study participation for a patient will be the earliest of date of death, date of withdrawal from further participation in the study, or date of safety follow-up visit (visit 801). For patients considered to be lost to follow-up, end of study participation will be the date of lost to follow-up reported by the investigator. Patient data included in database after the last date of study participation (date of death, date of early termination, or date of safety follow-up) will be excluded from statistical analysis. Listing of such data may be provided.

Summary statistics for categorical measures (including categorized continuous measures) will include sample size, frequency, and percentages. Summary statistics for continuous measures will include sample size, mean, standard deviation (SD), median, minimum, and maximum. The summary statistics will be presented by the nominal visit.

Statistical treatment comparisons will only be performed between tirzepatide doses and placebo. Since the trials are not adequately powered to detect differences among tirzepatide doses, comparisons among tirzepatide arms will not be performed unless otherwise specified.

Statistical summaries and results of statistical analysis will be displayed in the following treatment order: 5 mg tirzepatide, 10 mg tirzepatide, 15 mg tirzepatide, and placebo.

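### The hypoglycaemia incidence model has no rule for an arm without events: if no placebo patient has one, the odds ratio is infinite and Wald p-values and intervals are uninformative

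*SAP*

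**What the plan says.** SAP 6.13.2.1 (Hypoglycemic Events) fixes the model for incidence: "The incidence of hypoglycemic event will be analyzed using logistic regression with treatment and stratification factors as fixed effects". Its sparse-data rule is: "When the number of hypoglycemic events is less than 10, a listing of hypoglycemic events will be provided instead". The rule counts events, sets no minimum in any arm, and does not say whether the count is made within each category. The section names no test statistic, no penalised or exact method, and no step for an arm with no events. It also narrows what is counted: "Statistical summaries and analyses will exclude hypoglycemic events occurring after initiation of a new antihyperglycemic therapy".

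The same section provides incidence and rate by treatment for Level 2 and severe hypoglycaemia, and a listing of events.

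Placebo is the reference for every contrast (SAP 6.2): "Statistical treatment comparisons will only be performed between tirzepatide doses and placebo". Protocol 10.3.1 sets the default level: "all tests of treatment effects will be conducted at a 2-sided alpha level of 0.05". Its general rule for categorical data is that Fisher's "exact test will be used to examine the treatment difference in categorical outcomes"; it mentions logistic regression only as an option for binary efficacy outcomes. Protocol 10.3.4.1 asks for hypoglycaemia incidence to be compared between doses and placebo but names no test.

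Two general SAP clauses also apply. SAP 6.2 lets analyses be dropped when there are too few events, with a listing instead. SAP 6.13 lets summary tables be omitted, with patient-level listings, when fewer than 10 patients have the event. Both are discretionary.

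**The concern.** Patients enter on diet and exercise alone, with no oral agent in the preceding 3 months (Protocol 6.1), and events after any new antihyperglycaemic therapy are excluded. Protocol 3.2 reports that no group had severe hypoglycaemia in the earlier studies it describes. A placebo arm with no Level 2 or severe events is therefore plausible.

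Because placebo is the common reference, one empty arm makes the treatment coefficient non-estimable for all three doses at once. The threshold does not prevent this: 10 events can all fall in the tirzepatide arms, and a few patients with repeated episodes can reach 10.

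The comparison at stake is a stated safety objective (SAP 4.4). It would break down in the data pattern that most favours placebo. The SAP anticipates sparse-event failure elsewhere: SAP 6.12.2.2 has a fallback for non-convergence of the longitudinal HbA1c-target model. Hypoglycaemia has none.

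**Working it through.** **Inputs.** 118 patients per arm (Protocol 5.2: "A total of approximately 472 patients (118 patients per treatment group) will be randomized"), allocated 1:1:1:1, two-sided 0.05. The documents give no hypoglycaemia rate, power or effect, so there is no stated figure to reproduce; event counts and placebo risks below are assumptions shown as ranges.

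**Step 1. Chance of an empty placebo arm.** P(0 of 118) = (1 − p)^118.

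| Assumed placebo risk | P(no patient with an event) |
|---|---|
| 0.2% | 0.79 |
| 0.5% | 0.55 |
| 1% | 0.31 |
| 2% | 0.09 |
| 5% | 0.002 |

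**Step 2. Maximum likelihood with 0/8/8/8 patients** (placebo, 5, 10, 15 mg; treatment-only model; 15 mg v placebo). The odds ratio is (8 × 118)/(110 × 0), which is infinite. The Newton iterations do not settle:

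| Iteration | Log odds ratio | SE | Wald p |
|---|---|---|---|
| 8 | 6.58 | 9.2 | 0.47 |
| 12 | 10.58 | 67.8 | 0.88 |
| 20 | 18.58 | 3,700 | 0.996 |

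The printed p-value reflects where the software stops, not the data.

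**Step 3. Other tests on the same counts.**
- Fisher, two-sided: p = 0.007.
- Firth: in this treatment-only model the estimate equals adding one half to each cell, (8.5 × 118.5)/(110.5 × 0.5) = 18.2; penalised likelihood-ratio p = 0.003.
- Ordinary likelihood ratio: 2 × {[8 ln(8/118) + 110 ln(110/118)] − [8 ln(8/236) + 228 ln(228/236)]} = 11.37 on 1 df, p = 0.0007.

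**Step 4. Other counts.**

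| Placebo v 15 mg | Wald (8 to 20 iterations) | Fisher | Firth | Likelihood ratio |
|---|---|---|---|---|
| 0 v 6 | 0.49 to 0.996 | 0.029 | 0.012 | 0.0036 |
| 0 v 8 | 0.47 to 0.996 | 0.007 | 0.003 | 0.0007 |
| 0 v 10 | 0.46 to 0.996 | 0.0016 | 0.0007 | 0.00016 |

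**Step 5. One placebo event.** With 1 v 8 the log odds ratio is ln[(8 × 117)/(110 × 1)] = 2.14, SE = √(1/8 + 1/110 + 1/1 + 1/117) = 1.07, Wald p = 0.045. With 1 v 10, Wald p = 0.024 (Fisher 0.010). Removing the single placebo event makes the imbalance larger, yet the Wald p-value rises to 0.46 or more.

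**Step 6. Stratification factors.** With simulated strata (assumed: 4 countries, 30% high HbA1c, 45% prior oral therapy) and 0/10/10/10, Wald p at 25 iterations was about 0.9996 in all 200 data sets, and the likelihood-ratio p never exceeded 0.0005. At 25 iterations the treatment-only model also gives 0.9996. Adjustment neither causes nor cures the problem.

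**The case against.** The strongest reply is that the SAP says only logistic regression. It does not name the Wald test or require unpenalised likelihood. Firth's method is itself logistic regression, and the likelihood-ratio test from the ordinary model finds the imbalance. This stands: a reader might infer that the plan commits the sponsor to reporting a clear imbalance as non-significant, and the text does not support that. What remains is that the choice is unspecified and that Wald output is the usual default.

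A reader might also infer that a safety signal would be hidden. It would not: Level 2 and severe incidence are tabulated by arm and events are listed. Severe episodes are also serious adverse events, with their own summary, listing and narratives (SAP 6.13.1 and 6.13.1.2).

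Nor is the 10-event count the only safeguard. SAP 6.2 and 6.13 add sparse-data clauses, one of them counted in patients. But they are optional, and SAP 6.2 would remove the comparison rather than supply a valid one.

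Two further readings go too far. Strata with no events do not themselves break the treatment estimate: in a check with 1/8/8/8 events of 60 per arm in one country, adding a second, event-free country left the log odds ratio at 2.206 (SE 1.078, p = 0.041). And Fisher's test is the protocol's general rule for categorical outcomes, not a test assigned to this endpoint.

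**Conclusion.** The point holds as a gap in specification with a real numerical consequence. From 10 events onwards the SAP requires a model that has no finite estimate when the placebo arm is empty, and it names no alternative. In that case all three dose contrasts lack a finite odds ratio, and Wald p-values and intervals carry no information: 0.47 to 0.996 for 0 v 8, against 0.007 or less from Fisher, Firth or the likelihood ratio.

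This rests on two conditions. The first is exactly zero placebo patients with an event in the category analysed. That is plausible for Level 2 or severe events if placebo risk is about 1% or less, and unlikely at 5%; the documents give no rates. It is a stronger assumption for a category using the 70 mg/dL limit. The second is that Wald output is what gets reported. The efficacy conclusions are not affected.

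**What to change.** In SAP 6.13.2.1, prespecify Firth penalised logistic regression with profile-likelihood p-values and confidence intervals for hypoglycaemia incidence. Alternatively, keep ordinary logistic regression and switch to Fisher's exact test, the protocol's general rule for categorical outcomes, when any arm has zero or few patients with an event, with that number stated in advance. Set the listing threshold within each category in patients with an event, in line with SAP 6.13.

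The cost is a few sentences of SAP text and a procedure option; no new data or design change is needed. The downside is slight shrinkage of the estimates under Firth, or loss of stratum adjustment if Fisher's test is used.
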